## **Intervention**

The intervention will be based on a rehabilitation program approved by the MOH. (24) The rehabilitation sessions will include breathing techniques, aerobic exercises, strength training, and education. As part of the regular rehabilitation protocol, each participant will undergo the following rehabilitation program with a specialized licensed clinician.

### **1. Respiratory Exercises**

- Active cycle of breathing technique (ACBT)

The participants will start with exercises 1-3 at least twice a day and increase the frequency to four to six times a day. The exercises will include three stages: breathing control, chest expansion, and exhalation. Breathing control will be achieved by asking the participants to breathe in and out gently through the nose if possible. If the breath is exhaled through the mouth, the participant will be instructed to purse their lips as if they were blowing out a candle. The participant will be asked to try to gradually make their breathing slower. Following that, the participant will be instructed to take a long, slow, deep breath in through their nose if they can while keeping their chest and shoulders relaxed, then breathe out gently without forcing the air out and relax, as if sighing. Finally, they will be asked to “huff”, which is exhaling through an open mouth and throat instead of coughing. This helps move sputum up the participant’s airways so that they can be cleared in a controlled way. To “huff,” they must quickly squeeze air from their lungs and let it out through their open mouth and throat, as if they were trying to mist up a mirror or their glasses. They will be asked to use their abdominal muscles to help them squeeze the air out, but not to force it so much that they cause wheezing or tightness in their chest. If huffing clears their sputum, then they should not need to cough. They should only cough if the sputum can be cleared easily. They should continue the breathing exercises for about 10 minutes, ideally until their chest feels clear of sputum.

### **2. Aerobic exercises**

The aerobic exercises will include walking up and down stairs, walking at home, cycling, and dancing. Each session should last for 30–60 minutes per day and start with low-intensity exercise. The intensity will be increased by 10% every week. A limit of 70% of the maximum heart rate will be set. (25)

### **3. Progressive strengthening training**

Strengthening exercises are designed to improve muscle strength and endurance. The frequency and intensity will be adjusted for each participant individually. The participants will be requested to perform the following strengthening exercises. Standing heel raise: the participant should hold on to a chair, reach overhead while standing on their toes and bring their hands together. This should initially be repeated two to three times, increasing gradually to eight times (for one set). Mini squats should be performed while holding onto a chair and breathing. Wall push-ups should be held for eight seconds. Core exercises should start with 10–15 repetitions and then repetitions should slowly be increased. Participants should perform sit to stand

exercises for one minute. All these exercises should initially be repeated two to three times per day and frequency should be increased gradually to 10 times a day.

4. Mobility training or gait training to increase endurance.

Every day, participants will be asked to walk for at least 30 minutes without stopping as part of a mobility training program to improve endurance. Participants will also begin walking on flat surfaces before progressing to uneven surfaces. As the participants' mobility progresses and they gain endurance, they will be asked to challenge themselves by walking on hills and inclines for 10 minutes, increasing the frequency of this exercise to three times a day. They will be asked to walk five times per week, ascending and descending stairs with assistance if needed.

5. Home-exercise program (HEP)

All the activities, including a walking program, resistance exercises, and breathing techniques, should be continued at home.

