**Procedures:**

The research team will provide a full explanation of the study design, methods, and protocols to each participant. Informed consent then will be signed by the participants before starting the study.

The following safety precautions will be observed when assessing and training the participants. A safety belt will be placed around the participants' hips if needed. The participants will be requested to place their arms around the therapist's hips if they need to stand or walk. Therapists should avoid lifting the participants unless they ask for additional assistance. The participants should be given time to stand using their own strength. The therapists should stay close to the participants during transfer and walking, and the participants' weight should be kept close to the therapist's center of gravity to avoid falling. When the participants feel fatigued, the assessment of their training should cease immediately, and the participants should be given the opportunity to take a rest. After each assessment and training session, the participants should be given a two-to-three-minute break. Furthermore, the therapists must be closely supervised by an investigator to ensure that all research activities are carried out in accordance with the approved study protocols.

After signing the informed consent, the participants will answer this questionnaire.

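### The walking instruction asks for at least 30 minutes non-stop and continues at home, but the protocol's only stop-and-rest rule for fatigue is written for a therapist who is present

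*Combined protocol and SAP*

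**What the plan says.** All references are to the combined protocol and SAP.

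- **Walking dose.** The mobility or gait training item (item 4, printed after Progressive strengthening training) states: "Every day, participants will be asked to walk for at least 30 minutes without stopping". Progression is by terrain: "Participants will also begin walking on flat surfaces before progressing to uneven surfaces". Hills and inclines follow. The same paragraph later gives a frequency of five times a week, in a sentence that goes on to stairs.
- **Home.** The home-exercise item (item 5) states: "All the activities, including a walking program, resistance exercises, and breathing techniques, should be continued at home".
- **Fatigue rule.** Procedures opens its safety text with "The following safety precautions will be observed when assessing and training the participants". It includes "The therapists should stay close to the participants during transfer and walking" and then "When the participants feel fatigued, the assessment of their training should cease immediately", adding that "the participants should be given the opportunity to take a rest". The same paragraph covers a safety belt, help with standing and walking, and supervision of therapists by an investigator.
- **Aerobic exercise.** "The aerobic exercises will include walking up and down stairs, walking at home, cycling, and dancing". Sessions last 30 to 60 minutes a day, start at low intensity, and are capped at 70% of maximum heart rate.
- **Schedule.** Study Setting and duration gives three 45-minute sessions a week for four weeks.
- **Source programme.** Intervention says the content is based on a rehabilitation programme approved by the MOH and is delivered by a specialised licensed clinician.

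**The concern.** A participant who tires on a walk meets two instructions that point in different directions: keep going for the full half hour, or stop and rest. In a clinic session the therapist resolves this on the spot. At home the participant has only the programme's wording, and the part of it that addresses walking asks for no break.

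The eligible population makes this more than a drafting nicety. On walking ability, the exclusion criteria remove only patients who cannot walk at all. Someone who can walk, but not for 30 continuous minutes, can therefore enrol unless another exclusion applies. Procedures itself plans for participants who need physical help to stand or walk. Followed to the letter at home, the text is less protective than the protocol's own clinic rule. The stake is participant safety and a clear description of the intervention. No endpoint or analysis is affected.

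**Working it through.** The plan states no figure to reproduce on this point. The check has two parts.

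**1. Does any text carry the fatigue rule home?**

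| Section | What it controls | Rest rule for home walking? |
|---|---|---|
| Procedures | Precautions during assessment and training, built around a therapist in attendance | Not stated; home neither included nor excluded |
| Aerobic exercises | Intensity (low start, heart-rate cap); duration of 30 to 60 minutes; names walking at home | No |
| Item 4, mobility | Duration of at least 30 minutes without a break; progression by terrain | No |
| Item 5, home programme | Continues all activities | No |
| Exclusion criteria | Who enters | Not applicable |

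No section shown extends the rule. The aerobic section also sets a second 30-minute floor for walking at home, so amending item 4 alone would leave that floor unqualified.

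**2. How much prescribed walking falls outside clinic sessions?**

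Inputs: 4 weeks and 3 sessions a week (Study Setting and duration); a 30-minute minimum and a daily frequency (item 4); the alternative frequency of five a week (item 4).

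Assumptions: each clinic session contains at most one full prescribed walk; on the second reading, each walk lasts 30 minutes.

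Clinic sessions: 4 × 3 = 12.

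*Daily reading*
- Walks: 4 × 7 = 28
- Outside sessions: 28 − 12 = 16; 16/28 = 57%
- Minutes: 16 × 30 = 480 of 28 × 30 = 840

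*Five-times-weekly reading*
- Walks: 4 × 5 = 20
- Outside sessions: 20 − 12 = 8; 8/20 = 40%
- Minutes: 8 × 30 = 240 of 20 × 30 = 600

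Both are lower bounds. They credit every session with a full walk, yet a 30-minute walk would leave only 45 − 30 = 15 minutes for breathing, strengthening and education. If two sessions fall on one day, more days have no session.

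These figures count exposure to the instruction, not harm. How many participants would tire on a home walk cannot be computed from the documents.

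**The case against.** The case against has several parts, and much of it stands.

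- **Procedures may already apply.** Its precautions cover training, item 4 is training, and resting when tired needs no therapist. It is true that home is not excluded. But the rule sits among precautions that do need a therapist, and the home item does not refer back to it.
- **The wording describes a task.** A reader might infer that participants are told to push on through fatigue. The documents do not say so. They ask for continuous walking and are silent on what to do when tired at home. The fatigue rule is itself loosely worded, since it literally stops the assessment of training, so neither sentence should be pressed too hard.
- **Home walking is not without limits.** A reader might infer that it is. In fact the aerobic section starts at low intensity with a heart-rate cap and names walking at home. Walking begins on flat ground. Cardiovascular instability and pulmonary embolism are exclusions. Participants are 18 to 45 years old and 3 to 6 months past discharge. These limit intensity and entry; they do not supply a rest rule.
- **The MOH programme may hold the rule.** This cannot be settled from the documents.
- **The lack of a shorter starting duration is a defect.** A reader might infer this too. It is a choice of exercise prescription in a programme based on one that is not available here, and the documents do not show the choice to be wrong.
- **Measuring fatigue shows that it is expected.** The Fatigue Assessment Scale measures chronic fatigue symptoms. It does not show that the protocol expects exertional fatigue on a 30-minute walk, so the point does not rely on it.

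**Conclusion.** The point holds as a wording conflict that is cheap to remove. The instruction to walk without a break continues at home, and the only stop-and-rest rule is written for supervised work and is not carried over.

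At least 40% to 57% of prescribed walks fall outside clinic sessions, depending on which frequency governs. The 57% figure should not be cited alone: it needs the daily reading, and the sentence giving five times a week may or may not refer only to stairs. The conflict remains on either reading.

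The conclusion rests on the text shown. It would fall away in substance if the MOH programme already contains a home rest rule that participants receive; the remedy would then be to state that rule in the protocol. The documents do not support any claim of demonstrated harm or of damage to the trial's results.

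**What to change.** Three small wording changes:

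1. **Home-exercise item:** add *At home, as in the clinic, participants stop and rest when they feel fatigued.*
2. **Mobility item:** make 30 continuous minutes a target, subject to that rule.
3. **Aerobic exercises:** put the same qualifier on the 30 to 60 minute duration where it applies to walking at home.

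If the MOH programme already has such a rule, state that rule instead. These changes work under either walking frequency and do not need that ambiguity settled.

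A shorter starting duration set by the treating clinician is optional. It alters the dose, so it should be checked against the MOH programme first.

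**Cost:** one sentence added and two qualified, with no new visit, test, staff or eligibility change. The walking dose delivered will vary slightly more between participants, and the ethics committee must be notified of the wording change.

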## **Data analysis**

### **Sample size**

The required sample size was estimated from the percentage of the total population referred to the post-COVID centers using a confidence level of 95% and a confidence interval of 5%, resulting in an estimate of 60 participants with a 30% dropout rate.

### **Statistical analysis**

The data will be analyzed using multivariate statistics to compare more than two variables at baseline and afterward. Continuous variables will allow a mean to be obtained with standard deviation (normal data) or a median with an interquartile range (skewed data), while categorical variables will be obtained as numbers and percentages. The score data from the 6MWT, 10MWT, TUG, and STS tests will be examined using a paired t-test or a Wilcoxon signed rank test to facilitate comparison of matched pre-test and post-test scores, in addition to observations of the behavior and differences in the survey data.

## **Ethical approval:**

The study was approved by King Fahad Medical City (KFMC) in Riyadh, Saudi Arabia under IRB Log Number: 22-472E.
